### **5.2.3 Assessment of safety laboratory parameters**

For the assessment of laboratory parameters, blood and urine samples will be collected by the trial site at the time points indicated in the [Flow Chart](#) after the subjects have fasted for at least 10 h. Overnight fasting is not required at the discretion of the investigator or designee for retests.

The parameters that will be determined are listed in [Tables 5.2.3: 1](#) and [5.2.3: 2](#). Reference ranges will be provided in the ISF, [Section 10](#).

Manual differential white blood cell count or urine sediment examinations will only be performed if there is an abnormality in the automatic blood cell count or in the urinalysis, respectively.

Proprietary confidential information © 2017 Boehringer Ingelheim International GmbH or one or more of its affiliated companies

Table 5.2.3: 1

Routine laboratory tests

Functional lab group	Test name
Haematology	Haematocrit Haemoglobin Red blood cell count (RBC) Reticulocyte count White blood cell count (WBC) Platelet count Neutrophils, eosinophils, basophils, monocytes, lymphocytes
Automatic WBC differential (relative and absolute cell count)	
Manual differential WBC (if automatic differential WBC is abnormal)	Neutrophils (stabs), eosinophils, basophils, monocytes, lymphocytes
Coagulation	Activated partial thromboplastin time (aPTT) Prothrombin time (Quick's test and INR) Fibrinogen
Enzymes	Aspartate transaminase (AST/GOT) Alanine transaminase (ALT/GPT) Alkaline phosphatase (AP) Gamma-glutamyl transferase (GGT) Creatine kinase (CK) CK-MB Lactate dehydrogenase (LDH) Serum tryptase  Thyroid stimulating hormone (TSH) fT 3 , fT 4
Hormones 	
Substrates	Plasma glucose Creatinine Total bilirubin Direct bilirubin Total protein Protein electrophoresis (only at screening examination)  Albumin Alpha-1-Globulin Alpha-2-Globulin Beta-Globulin Gamma-Globulin C-Reactive Protein (CRP) Uric acid Total cholesterol Triglycerides Sodium Potassium Chloride Calcium Inorganic phosphate
Electrolytes	

Proprietary confidential information © 2017 Boehringer Ingelheim International GmbH or one or more of its affiliated companies

**Table 5.2.3: 1**      **Routine laboratory tests (cont).**

Functional lab group	Test name
Urinalysis (Stix)	Urine nitrite Urine protein Urine glucose Urine ketone Urobilinogen Urine bilirubin Urine erythrocytes Urine leukocytes Urine pH
Urine sediment (microscopic examination if urine analysis abnormal)	Only positive findings will be reported (for instance, the presence of sediment bacteria, casts in sediment, squamous epithelial cells, erythrocytes, leukocytes)

 Only at screening

The tests listed in [Table 5.2.3: 2](#) are exclusionary laboratory tests which may be repeated as required. The results will not be entered in the CRF/database and will not be reported in the CTR. Except for pregnancy test and drug screening, it is planned to perform these tests during screening only. Pregnancy testing in women will be performed at screening, prior to treatment, and as part of the end of trial examination. Drug screening will be performed at screening and at admission to the trial site the day prior to treatment.

**Table 5.2.3: 2**      **Exclusionary laboratory tests**

Functional lab group	Test name
Drug screening (urine)	Amphetamine/MDA Barbiturates Benzodiazepine Cannabis Cocaine Opiates
Infectious serology (blood)	Hepatitis B surface antigen (qualitative) Hepatitis B core antibody (qualitative) Hepatitis C antibodies (qualitative) HIV-1 and HIV-2 antibody (qualitative)

To encourage compliance with alcoholic restrictions, a breath alcohol test (Dräger Alcotest® 6510 and Alcotest® 5510, Belgium) will be performed at screening and at the start of the in-house period (Day -1) and may be repeated at any time during the study at the discretion of an investigator or designee. The results will not be included in the CTR.

In case of a potential systemic allergic reaction, blood samples for determination of serum tryptase will be collected 0.5 h, 2 h, 6 h, and 24 h after onset of the event.

The laboratory tests listed in [Table 5.2.3: 1](#) and [5.2.3: 2](#) will be performed ZNA Klinisch Laboratorium, Antwerpen, Belgium with the exception of the drug screening and pregnancy

Proprietary confidential information © 2017 Boehringer Ingelheim International GmbH or one or more of its affiliated companies

tests. These tests will be performed at the trial site using 'Alere Triage TOX Drug Screen' and MAHSAN® -HCG rapid test or equivalent, respectively.

Laboratory data will be transmitted electronically from the laboratory to the trial site.

Samples for cytokine analysis (cytokines IL1 $\beta$ , IL6, TNF- $\alpha$ , and IFN $\gamma$ ) will be collected at baseline, 4h, and 24h postdose. The cytokine samples will be only analysed in case of specific adverse events suggestive for cytokine release.

#### **5.2.4      Electrocardiogram**

##### **5.2.4.1      12-lead resting ECG**

Twelve-lead ECGs (I, II, III, aVR, aVL, aVF, V1 - V6) will be recorded using a computerised electrocardiograph (MAC 5500, GE Healthcare) at the time points given in the [Flow Chart](#).

In order to achieve a stable heart rate at rest and to assure high quality recordings at comparable resting phases, all ECGs will be recorded for a 10-sec duration after the subjects have rested for at least 5 min in a supine position. The site personnel will be instructed to assure a relaxed and quiet environment so that all subjects are at complete rest during the recordings. ECG assessment will always precede all other study procedures of the same time point (except blood drawing from an intravenous cannula which is already in place) to avoid impact of sampling on the ECG quality.

Electrode placement will be performed according to the method of Wilson, Goldberger.

All locally printed ECGs will be evaluated by the investigator or a designee.

ECGs may be repeated for quality reasons (like alternating current artefacts, muscle movements, electrode dislocation) and the repeated ECG will be used for analysis.

Additional (unscheduled) ECGs may be collected by the investigator for safety reasons. These ECGs are assigned to the prior scheduled time point. Unscheduled ECGs will not be included into the statistical analysis of interval lengths.

For the inclusion or exclusion (see [Section 3.3](#)) of a subject and for the assessment of cardiac safety during the study, the QT and QTcB values generated by the ECG machines or their manual corrections by the investigators will be used.

Abnormal findings will be reported as AEs (during the trial) or baseline conditions (at screening) if judged clinically relevant by the investigator. Any ECG abnormalities will be monitored carefully and, if necessary, the subject will be removed from the trial and will receive the appropriate medical treatment.

##### **5.2.4.2      Continuous ECG monitoring and oxygen monitoring**

Cardiac rhythm (including heart rate) will be monitored by means of continuous 2-lead ECG recording for at least 15 min before (for baseline assessment) and 2 h following the start of IV infusion or SC injection using the Dräger Telemetry monitoring system, Infinity M300. Oxygen saturation will be monitored by pulse oximetry using either Type NT1 handheld pulse oximeter from Newtech or Oxytrue A from Bluepoint Medical.

## **5.2.5 Assessment of other safety parameters**

### **5.2.5.1 Vital signs**

Systolic and diastolic blood pressures (BP) as well as pulse rate (PR) or heart rate (heart rate is considered to be equal to pulse rate) will be measured by a blood pressure monitor (Welch Allyn 530TP and 530TO devices) at the times indicated in the [Flow Chart](#), after subjects have rested for at least 5 min in a supine position. All recordings should be made using the same type of blood pressure recording instrument on the same arm if possible.

### **5.2.5.2 Medical examinations**

At screening, the medical examination will include demographics including height and body weight, smoking and alcohol history, relevant medical history and concomitant therapy, review of inclusion and exclusion criteria, review of vital signs (BP, PR), 12-lead ECG, laboratory tests, and a physical examination. At the end of trial examination, it will include review of vital signs, 12-lead ECG, laboratory tests, and a physical examination with determination of weight.

### **5.2.5.3 Local tolerability**

Local tolerability will be assessed by the investigator according to 'swelling', 'induration', 'heat', 'redness', 'pain', or 'other findings'.

### **5.2.5.4 Oral body temperature**

Oral body temperature will be measured at the times indicated in the [Flow Chart](#) using a standard device.

## **5.3 OTHER**

### **5.3.1 Pharmacogenomic evaluation**

Not applicable.

### **5.3.2 Other endpoints**

Not applicable.

### **5.3.3 Other assessments**

Not applicable.

## **5.4 APPROPRIATENESS OF MEASUREMENTS**

All measurements performed during this trial are standard measurements and will be performed in order to monitor subjects' safety and to determine pharmacokinetic parameters in an appropriate way. The scheduled measurements will allow monitoring of changes in vital signs, standard laboratory values, and ECG parameters that might occur as a result of

Proprietary confidential information © 2017 Boehringer Ingelheim International GmbH or one or more of its affiliated companies

administration of trial medication. The safety assessments are standard, are accepted for evaluation of safety and tolerability of an IV and SC administered drug, and are widely used in clinical trials. The pharmacokinetic parameters and measurements outlined in [Section 5.5](#) are generally used assessments of drug exposure.

## **5.5 DRUG CONCENTRATION MEASUREMENTS AND PHARMACOKINETICS**

Date and clock time of drug administration and pharmacokinetic sampling will be recorded in the CRFs.

Exact time points of plasma sampling will be derived from the electronic data capturing system LabPas and documented in the CRFs by the medical personnel or sent as electronic files to the trial data manager. The actual sampling times will be used for determination of pharmacokinetic parameters.

### **5.5.1 Pharmacokinetic endpoints**

#### **5.5.1.1 Primary endpoints**

The following primary endpoints will be determined for BI 655130:

- $AUC_{0-tz}$  (area under the concentration-time curve of the analyte in plasma over the time interval from 0 to the last quantifiable data point)
- $C_{max}$  (maximum measured concentration of the analyte in plasma)

#### **5.5.1.2 Secondary endpoint**

The following secondary endpoint will be evaluated for BI 655130:

- $AUC_{0-\infty}$  (area under the concentration-time curve of the analyte in plasma over the time interval from 0 extrapolated to infinity)

## **5.5.2        Methods of sample collection**

### **5.5.2.1      Plasma sampling for pharmacokinetic analysis**

For quantification of BI 655130 plasma concentrations, approximately        of blood will be taken from an antecubital or forearm vein into a K2EDTA (ethylenediaminetetraacetic acid) anticoagulant blood drawing tube at the times indicated in the [Flow Chart](#) under 'Plasma PK'. Blood will be withdrawn by means of either an indwelling venous catheter or by venipuncture with a metal needle.

The K2EDTA-anticoagulated blood samples will be mixed gently and placed on ice until centrifugation for about 10 minutes at about 2000 g to 4000 g and at approximately 4°C. The blood should be centrifuged to produce plasma as soon as possible after collection, but not later than 30 minutes after withdrawal. Two aliquots of EDTA plasma sample will be obtained in two labelled polypropylene cryotubes. At a minimum, the sample tube labels should list the following information: BI trial number, subject number, visit, PTM, aliquot #1 or #2, plasma, and PK.

The two aliquots should contain approximately        of plasma each. The plasma samples will be stored in a freezer at about -20°C or below at the clinical site until shipment to the analytical laboratory.

After completion of the trial, the plasma samples may be used for further methodological investigations, e.g. for stability testing. However, only data related to the analyte will be generated by these additional investigations. The study samples will be discarded after completion of the additional investigations but not later than 5 years after the final study report has been signed

### **5.5.3      Analytical determinations**

#### **5.5.3.1    Analytical determination of BI 655130 plasma concentration**

BI 655130 concentrations will be determined by a validated Enzyme Linked Immunosorbent Assay (ELISA).

## 6. INVESTIGATIONAL PLAN

### 6.1 VISIT SCHEDULE

Exact times of measurements outside the permitted time windows will be documented. The acceptable time windows for screening and end of trial examination are given in the [Flow Chart](#).

Study measurements and assessments scheduled to occur 'before' trial medication administration on Day 1 are to be performed and completed within a 3 h-period prior to the trial drug administration (including blank values for PK).

The acceptable deviation from the scheduled time for vital signs and ECG will be:

- $\pm 15$  min up to including 12 h
- $\pm 30$  min from 12h up to including 48 h
- $\pm 120$  min from 48 h up to Day 8
- $\pm 48$ h from Day 9 up to Day 14
- $\pm 72$ h from >Day 14 up to the last measurements

If scheduled in the [Flow Chart](#) at the same time as a meal, blood sampling, vital signs, and 12-lead ECG recordings have to be done first. Furthermore, if several measurements including venipuncture are scheduled for the same time, venipuncture should be the last of the measurements due to its inconvenience to the subject and possible influence on physiological parameters.

For planned individual plasma concentration sampling times refer to the [Flow Chart](#). While these nominal times should be adhered to as closely as possible, the actual sampling times will be recorded and used for the determination of pharmacokinetic parameters.

If a subject misses an appointment, it will be rescheduled if possible. The relevance of measurements outside the permitted time windows will be assessed no later than at the Report Planning Meeting.

### 6.2 DETAILS OF TRIAL PROCEDURES AT SELECTED VISITS

#### 6.2.1 Screening period

After having been informed about the trial, all subjects will give their written informed consent in accordance with GCP and local legislation prior to enrolment in the study.

For information regarding laboratory tests (including drug and virus screening), ECG, vital signs, and physical examination, refer to [Sections 5.2.3](#) to [5.2.5](#).

#### 6.2.2 Treatment period

Study participants will be admitted to the trial site in the evening of Day -1 and kept under close medical surveillance for at least 48 h following drug administration. The subjects will then be allowed to leave the trial site after formal assessment and confirmation of their fitness. On all other study days, the study will be performed in an ambulatory fashion.

Proprietary confidential information © 2017 Boehringer Ingelheim International GmbH or one or more of its affiliated companies

Details on treatments and procedures of administration are described in [Section 4.1.4](#).

For details on time points and procedures for collection of plasma samples for PK analysis, refer to [Flow Chart](#) and [Section 5.5.2](#).

The safety measurements performed during the treatment period are specified in [Section 5.2](#) of this protocol and in the [Flow Chart](#). For details on time points for all other trial procedures, refer to the [Flow Chart](#). AEs and concomitant therapy will be assessed continuously from screening until the end of trial examination.

### **6.2.3      End of trial period**

For AE assessment, laboratory tests, collection of PK samples, recording of ECG and vital signs, and physical examination during the end of trial period, see [Sections 5.2.2](#) to [5.2.5](#).

Subjects who discontinue treatment before the end of the planned treatment period should undergo the end of trial visit.

All abnormal values (including laboratory parameters) that are judged clinically relevant by the investigator will be monitored using the appropriate tests until a return to a medically acceptable level is achieved. (S)AEs persisting after subject's end of trial must be followed up until they have resolved, have been sufficiently characterised, or no further information can be obtained.

The end of the trial as a whole is defined by the 'last regular visit completed by last subject' or 'end date of the last open AE' or 'date of the last follow-up test' or 'date of an AE has been decided as sufficiently followed-up', whichever is latest.

## 7. STATISTICAL METHODS AND DETERMINATION OF SAMPLE SIZE

### 7.1 STATISTICAL DESIGN – MODEL

#### 7.1.1 Objectives

The primary objective of this trial is to investigate the relative bioavailability of \_\_\_\_\_ of BI 655130 following subcutaneous administration (Test, T) compared to \_\_\_\_\_ of BI 655130 following intravenous infusion (Reference, R). This will be evaluated statistically by use of an appropriate linear model.

The secondary objective is the evaluation and comparison of several pharmacokinetic parameters between all tested treatments. The secondary objective will be assessed by descriptive statistics.

The assessment of safety and tolerability is an additional objective of this trial, and will be evaluated by descriptive statistics.

#### 7.1.2 Endpoints

Relative bioavailability is to be determined on the basis of the primary and secondary pharmacokinetic endpoints (see [Section 5.5.1](#)).

Safety and tolerability will be determined on the basis of the parameters specified in [Section 5.2.1](#).

#### 7.1.3 Model

The statistical model used for the inter-individual comparison of the primary and secondary endpoints following SC versus IV administration of \_\_\_\_\_ of BI 655130 will be an ANOVA (analysis of variance) model on the logarithmic scale, accounting for the treatment group as a source of variation. The effect ‘treatment group’ will be considered as fixed. The model is described by the following equation:

$y_{ij} = \mu + \tau_i + e_{ij}$ , where

$y_{ij}$  = logarithm of response (endpoint, see [Section 7.1.3](#)) measured on subject j receiving treatment i

$\mu$  = overall treatment mean,

$\tau_i$ : effect of treatment i

$e_{ij}$  = the random error associated with the subject j who received treatment ,

where  $e_{ij} \sim N(0, \sigma^2)$  where  $\sigma^2$  is the total variability

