### 3. DESCRIPTION OF DESIGN AND TRIAL POPULATION

#### 3.1 OVERALL TRIAL DESIGN AND PLAN

This study will explore the safety, tolerability, and pharmacokinetics of a newly developed SC formulation of BI 655130 at two different dose strengths of and in an open-label, sequential group design. Furthermore, the relative bioavailability of the SC dose (Test) will be compared with one single IV dose of BI 655130 (Reference) in an open-label, , parallel group design). For details refer to [Section 4.1](#). Each participating subject will receive only one dose. Subjects assigned to the IV dose will be matched for gender and body weight ( $\pm 10\%$ ) to subjects receiving the SC dose.

The study will start with the lowest SC dose of of BI 655130. The dose group will be divided into 2 cohorts: on the first study day, 6 subjects will be treated, with an interval between the injections of at least 15 min. The second cohort will be treated at least 48 h apart. There will be an interval of at least 1 week after the first dosing in the SC dose group before the start of the SC or IV dose groups in a randomised sequence (in one week 6 subjects on IV and 6 subjects on SC and in the following week again 6 + 6). No more than 2 subjects should simultaneously receive an IV infusion. At any time during the ongoing study, further dosing will be stopped in case of safety and tolerability concerns based on the pre-specified trial-specific stopping criteria ([Section 3.3.4.2](#)).

A documented Safety Review must take place prior to dose escalation to Furthermore, an unscheduled safety review meeting can be requested anytime for any reasonable cause by the Principal Investigator (or an authorised deputy) or the sponsor of the study, e.g. because of any unforeseen adverse events. Dose escalation will only be permitted if no safety concerns exist in the opinion of the Principal Investigator (or an authorised deputy) and the trial clinical monitor (or an authorised deputy). In addition, at least 6 evaluable subjects per dose level are required to decide about dose escalation to the dose level.

The minimum data set for review consists of the following data:

- AEs (including clinically relevant findings from ancillary safety testing listed below) (Note: AEs may be ongoing at the time of Safety Reviews and AE information may be subject to change prior to Database Lock)
- Results from 12-lead ECG and continuous ECG monitoring
- Vital signs
- Clinical laboratory tests

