### **3.3 SELECTION OF TRIAL POPULATION**

It is planned that 36 healthy male and female subjects (12 subjects per treatment group) will enter the study. They will be recruited from the volunteers' pool of the trial site. Healthy subjects of the IV dose group will be matched for gender and body weight ( $\pm 10\%$ ) to subjects of the SC dose group.

A log of all subjects enrolled into the trial (i.e. having given informed consent) will be maintained in the ISF at the investigational site irrespective of whether they have been treated with investigational drug or not.

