### **3.3.5 Replacement of subjects**

In case some subjects do not complete the trial, the trial clinical monitor together with the trial pharmacokineticist and the trial statistician are to decide if and how many subjects will be replaced. A replacement subject will be assigned a unique study subject number, and will be assigned to the same treatment as the subject he replaces.

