#### **4.1.2 Method of assigning subjects to treatment groups**

Prior to the screening visit, subjects will be contacted in writing and informed about the planned visit dates. The subjects willing to participate will be recruited to dose groups according to their temporal availability. As soon as enough subjects have been allocated to 1 of the 6 dose cohorts (2 cohorts per dose group), the following subjects will be allocated to one of the other dose cohorts. Therefore, the allocation of subjects to dose cohorts is not

Proprietary confidential information © 2017 Boehringer Ingelheim International GmbH or one or more of its affiliated companies

influenced by trial personnel, but only by the subjects' temporal availability. As the study includes healthy subjects from a homogenous population, relevant imbalances between the dose groups are not expected.

The list with study subject numbers and allocated treatments will be provided to the trial site in advance. The allocation of subjects to study subject numbers will be performed prior to the first administration of trial medication. For this purpose, the subjects will be allocated to a study subject number by drawing lots. Once a subject number has been assigned, it cannot be reassigned to any other subject.

The subject number procedure is described in [Section 7.5](#).

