## 7.2 NULL AND ALTERNATIVE HYPOTHESES

The relative bioavailability of BI 655130 following SC compared to IV administration will be estimated by the ratios of the geometric means (test/reference) for the primary and secondary PK endpoints. Additionally, their two-sided 90% confidence intervals (CIs) will be provided. This method corresponds to the two one-sided t-tests procedure, each at the 5% significance level. Since the main focus is on estimation and not testing, an acceptance range was not specified, that is, no hypothesis will be tested.

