### **7.4 PRIMARY ENDPOINTS**

Analysis of relative BA of primary endpoints  $AUC_{0-tz}$  and  $C_{max}$  of BI 655130 in plasma will be performed as defined in Sections 7.1.3 and 7.3.1 of the CTP.

The statistical model for the primary analysis (comparison of subcutaneous versus intravenous administration of [redacted] of BI 655130) is an ANOVA model on the logarithmic scale including an effect for "treatment group" as defined in Sections 7.1.3 and 7.3.1 of the CTP.

Primary PK endpoints will also be assessed descriptively. The analysis of standard PK parameters is performed according to BI standards ([5](#)) [001-MCS-36-472\_RD-01].

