### **7.8.5      Others**

Physical examination findings will be reported as relevant medical history/baseline condition (i.e., a condition already existent before intake of study drug) or as AE and will be summarised as such. No separate listing or analysis of physical examination will be prepared.

Matching pairs for subjects included in the      BI SC and      BI IV treatment group will be summarized in a table and a listing displaying the matching criteria.

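### Minor: IV subjects are matched to SC subjects on sex and body weight, but the primary ANOVA ignores both, so its 90% CI may be conservative and wider than the data need

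*Protocol*

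**What the plan says.** Protocol section 3.1 states: "Subjects assigned to the IV dose will be matched for gender and body weight", with a ±10% tolerance on weight. Section 3.3 ("Healthy subjects of the IV dose group will be matched for gender and body weight") and the synopsis repeat it. The SC dose label is blanked. By context the matched SC group is the Test arm of the primary comparison, and this note assumes so.

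Protocol section 7.1.3 specifies the primary model as a "model on the logarithmic scale, accounting for the treatment group as a source of variation". Its equation has an overall mean, a treatment effect and an error term, and the error variance is described as total variability. SAP 7.4 repeats it: the model "is an ANOVA model on the logarithmic scale including an effect for" treatment group. SAP 7.5.2 applies the same analysis to AUC0-∞, and SAP section 4 declares no departure from the protocol.

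The matching reappears only in SAP 7.8.5, where pairs for the SC and IV "treatment group will be summarized in a table and a listing displaying the matching criteria". No adjusted or paired analysis is planned, even as a sensitivity analysis.

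**The concern.** Matching is worthwhile only if sex and weight are expected to influence exposure. If they do, balancing them removes most of their variance from the difference between arm means. A treatment-only ANOVA still counts that variance in the residual that sets the interval. The standard error is then too large for the design actually used, and a nominal 90% interval covers more than 90%.

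The SC/IV ratio and its 90% CI are the trial's main output, so unnecessary width is a real if modest loss. The recruitment cost of matching would be paid without taking the precision it offers. The point estimate is not systematically biased by the omission.

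**Working it through.** **Inputs from the documents.** 12 subjects per arm, two-sided 90% CI, log scale (Protocol 7.2, 7.3.1, 7.5); gCV 15.6%, 12.7% and 7.17%, with 95% coverage probability for the precision figures (Protocol Table 7.5:1).

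**Inputs assumed.** R² of sex and weight for log exposure, 0 to 30%. For simulation: log-SD of weight 0.16, sex shift in log weight 0.20, about half female, effect acting through weight, matched weights uniform within ±10%, unmatched subjects drawn independently, total gCV 15.6%.

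**Step 1: reproduce the plan's figure.** At gCV 15.6%, σ = √ln(1 + 0.156²) = 0.1551. The half-width on the log scale is

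ω = t(0.95; 22) × σ × √(2/12) × √(χ²(0.95; 22)/22) = 1.717 × 0.1551 × 0.4082 × √(33.92/22) = 0.1350.

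Precision is exp(2ω) = 1.310, and the limits at a ratio of 100% are 87.37 to 114.45, as in Table 7.5:1. The other two gCVs also reproduce (1.246 and 1.133). The table therefore uses the unmatched formula, consistent with the planned model.

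**Step 2: approximate effect of full matching.** The variance of the treatment difference falls to about (1 − R²) of what the ANOVA assumes. Coverage is then about P(|t22| < 1.717/√(1 − R²)), which gives 91.6%, 93.2% and 94.8% at R² 10%, 20% and 30%. Adjusting for sex and log weight leaves 20 df. The width ratio, planned over adjusted, is about 1.717/(1.725 × √(1 − R²)) = 1.05, 1.11 and 1.19.

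**Step 3: simulation (12,000 replicates per cell), all 12 pairs matched.**

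| R² | Coverage, treatment-only | Mean half-width, treatment-only / adjusted | Ratio |
|---|---|---|---|
| 0 | 90% | 0.1077 / 0.1084 | 0.994 |
| 5% | 91% | 0.1078 / 0.1055 | 1.02 |
| 10% | 92% | 0.1083 / 0.1027 | 1.05 |
| 20% | 93% | 0.1087 / 0.0968 | 1.12 |
| 30% | 95% | 0.1091 / 0.0904 | 1.21 |

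Adjusted coverage stayed at 89.5% to 90.6% in all cells. The mean error of both estimators was within ±0.0015 on the log scale. In single trials the adjusted interval is still the wider one in 48%, 33% and 14% of cases at R² 5%, 10% and 20%.

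**Step 4: incomplete matching.**

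| Pairs matched | Treatment-only coverage at R² 20% | Cost of adjusting if R² = 0 | Break-even R² |
|---|---|---|---|
| 12 | 93.3% | 0.6% wider | about 1% |
| 10 | 92.8% | 1.3% | 2–3% |
| 6 | 91.4% | 2.9% | 5% |
| 0 | 90.1% | 5.4% | 10% |

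With no matching, treatment-only coverage is about 90% at every R². The adjusted interval is then 2.7% wider at R² 5%, equal at 10%, 6% narrower at 20% and 12% narrower at 30%.

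**Step 5: cost on the protocol's own criterion.** With 20 df, ω = 1.725 × 0.1551 × 0.4082 × √(31.41/20) = 0.1368, and precision is 1.315. That is 1.4% wider than planned if R² = 0 with full matching. Break-even is 1 − (0.1350/0.1368)², about 3%.

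**Step 6: size on the ratio scale.** At a true ratio of 100%, R² 20% and full matching, average limits move from 89.7–111.5 to 90.8–110.2 (gCV 15.6%) and from 95.1–105.1 to 95.6–104.6 (gCV 7.17%).

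**The case against.** The strongest reply is that both models are valid and the plan contains no mistake. The planned interval errs on the safe side, Table 7.5:1 matches the planned model, and the protocol regards the sample size as adequate for an exploratory trial. No acceptance range is set ("an acceptance range was not specified, that is, no hypothesis will be tested"), so nothing turns on a limit moving by about half to just over one percentage point. This stands, and it is why the point is minor.

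Second, the size rests on two unknowns. R² is not documented. Matching may also be incomplete: Protocol 4.1.2 has subjects "recruited to dose groups according to their temporal availability" and numbered by drawing lots, with no matching step. This stands too. Without matching the interval is not conservative, and what remains is ordinary covariate adjustment, which pays only above an R² of about 10%.

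Third, the SAP is final (06-FEB-18) and describes the study as already performed, and the trial is open throughout. A late switch of primary model could look data-driven. That limits the remedy but does not remove the point.

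Fourth, SAP 7.8.5 already tabulates the pairs. That covers part of the reporting request, but the section does not commit to a count of pairs meeting the criteria.

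**Conclusion.** The point holds as a minor, conditional one. The design matches on sex and weight, and the primary analysis makes no use of it. If all pairs are matched and R² is 10% to 30%, the nominal 90% CI covers about 92% to 95% and is about 5% to 20% wider than an adjusted interval from the same data. With half the pairs matched and R² 20%, coverage is 91.4% and the excess width about 9% (0.1076/0.0987). With R² zero or no matching, coverage is nominal.

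These sizes depend on the assumed R² range, the assumed weight distribution and sex mix, and the reading that the matched SC group is the Test arm. Unequal slopes do not undermine the adjustment under full matching. With the Test slope at 1.4 times and the Reference slope at 0.6 times the common slope, adjusted coverage stayed at 89.8% to 90.4%. The planning gCVs come from a male-only trial, while this one enrols both sexes. Sex and weight could therefore matter more here, but the documents give no figure.

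**What to change.** **If PK results have not been seen:** in Protocol 7.1.3 and SAP 7.4 and 7.5.2, prespecify log(PK) = μ + treatment + log(screening body weight) + sex + error for the Test/Reference ratio and its 90% CI. Keep the treatment-only ANOVA as a sensitivity analysis.

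**If they have:** leave the treatment-only ANOVA as primary and report the adjusted model as supportive.

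**In both cases:** add to the SAP 7.8.5 table the number of pairs that met both matching criteria, since the gain depends on it.

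A pair effect should not be the primary model. Pairs may never form under Protocol 4.1.2 or may break through PK exclusions. Under Protocol 3.3.5 a replacement "will be assigned to the same treatment as the subject he replaces", with no stated re-matching. A paired analysis also drops from 22 to 11 df.

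**Cost:** wording only, or one extra model. Sex and screening weight are already collected. The statistical price is 2 df and a common log-linear slope. If sex and weight explain nothing, the interval is about 0.6% wider on average with full matching (1.4% on the protocol's precision criterion) and about 5% wider with none.
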